### **Research Design and Methodology:**

Research design and general methodological approach: We will perform a randomized control trial comparing oral UPA to LNG-IUS for emergency contraception. We will prospectively enroll 532 women experiencing an act of under-protected intercourse within the previous 5 days (120 hours). Participants with a negative pregnancy test, and who meet all inclusion criteria, will be randomized to either an immediate LNG-IUS insertion or oral UPA EC regimen (30mg ulipristal acetate) in a 3:1 ratio. Participants will be provided with a pregnancy test to perform at home and will be called to report the results of the urine pregnancy test 5-6 weeks after insertion. Participants receiving the LNG-IUS will also be return for a brief visit to check LNG-IUS strings. Participants will be contacted via telephone at 6 and 12months post enrollment to complete a follow-up survey. The primary outcome of this study is observed pregnancy rates at 5 weeks and 6 months after enrollment.

Criteria for selection of subjects: Potential participants for this study will be identified in as follows: 1) Women enrolled in the Contraceptive CHOICE Project (CHOICE) who are not currently using a long acting reversible contraceptive (LARC) method and have experienced an act of under-protected intercourse in the previous 5

days; 2) Women presenting, either in person or via telephone contact, to the Barnes Jewish Hospital Women's Health resident OB/GYN clinic who have experienced an act of under-protected intercourse in the previous 5 days; 3) Women identified from an advertising campaign; and

Enrollment: All potential participants receive informed consent and will be directed to make an appointment for consent, randomization, and allocation of method.

Inclusion Criteria:

- Women age 14-45
- Under-protected intercourse within the last five days (120 hours)
- Willingness to accept either IUS intervention or oral EC
- Ability and willingness to follow-up via telephone for results of a urine pregnancy test (UPT)
- Ability and willingness to be contacted by phone for 6 and 12 month follow-up

Exclusion Criteria:

- Positive pregnancy test
- Non-English speaking
- Contraindication to intrauterine contraception or oral UPA
  - Active cervicitis, PID, or recent post-abortal or postpartum infection
  - Undiagnosed abnormal uterine bleeding
  - Known or suspected cervical or endometrial neoplasia

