#### Evaluation/ Follow-Up:

At enrollment all women will undergo a highly sensitive urine pregnancy test as well as self-collected vaginal swab for sexually transmitted disease (STI) testing for *Neisseria gonorrhoeae* and *Chlamydia trachomatis*. Randomization and allocation of emergency contraceptive method will occur immediately following consent. A positive test for an STI will not exclude the patient from participation. All positive *N. gonorrhoeae* or *C. trachomatis* tests will be treated with standard CDC-approved treatment. Partner treatment will also be offered. Women randomly assigned to the LNG-IUS group will be asked to return at 5-6 weeks for a string check. All participants will be provided a urine pregnancy test at enrollment and will be called at 5 weeks post enrollment to obtain results. Participants will then be contacted to complete a follow-up surveys at 6 and 12 months following enrollment.

Measures: Urine pregnancy test results will be documented at 5-6 weeks following method allocation. Negative urine pregnancy tests will be validated by a normal menses after enrollment. Participants testing positive at home will be asked to come into the study site for pregnancy test validation and options counseling. We have studied over 9,000 women attempting to avoid unintended pregnancy in the Contraceptive CHOICE Project. Participants were able and willing to report home pregnancy testing results and/or return for a visit for a sensitive pregnancy test. Any woman who suspects pregnancy, is late for her routine menstrual cycle, or who reports a positive home test will be asked to return to our clinic for pregnancy test validation and options counseling (offered option of continuing the pregnancy or pregnancy termination). *We are using the CONSULT urine pregnancy test which is sensitive to a hcg level of 20mIU/mL with a specificity of >99% (Appendix A).*

Women enrolled in an EC study are clearly motivated to avoid an unintended pregnancy. A negative home pregnancy test and regular menses reliably excludes an on-going pregnancy. Self-report of a negative test and menses will not be validated, as they are acceptable measures to reliably exclude pregnancy. Pregnancy

testing in this protocol has been used for the CHOICE project, with two peer-reviewed publications accepted to the New England Journal of Medicine (Winner B. et al. 2012 & Secura G. et al. 2014)

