**ADVERSE REACTIONS:** There are few side effects of UPA and LNG-IUS. These are listed in the protocol and informed consent form. Most side effects resolve spontaneously. Anticipated events means reactions to treatment previously observed that may require medical intervention but are not serious in nature.

All adverse events that occur will be recorded in the Source Documents. Adverse events should be captured in the medical history.

Adverse Events occurring will be captured and followed until the condition resolves, stabilizes, or is otherwise explained, or the subject is lost to follow-up. Subjects will be instructed that they may contact one of the Principal Investigator at any time throughout the course of the study.

The Investigator will review each event and assess its relationship to method of EC (not related, unlikely, possible, probable, and highly probable). The following definitions will be used for rating relationship to the treatments or investigational device:

- Not related – The event is clearly related to other factors such as the subject's clinical state, therapeutic interventions, or concomitant medications administered to the subject.
- Unlikely – The event was most likely produced by other factors such as the subject's clinical state, therapeutic interventions, or a concomitant medication administered to the subject; and does not follow a known response pattern to the investigational device.
- Possible – The event follows a reasonable temporal sequence from the time of investigational device administration; and/or follows a known response pattern to the study treatments; but could have been produced by other factors such as the subject's clinical state, therapeutic interventions, or concomitant medications administered to the subject.
- Probable – The event follows a reasonable temporal sequence from the time of investigational device administration; and follows a known response pattern to the investigational device; and cannot be reasonably explained by other factors such as the subject's clinical state, therapeutic interventions, or concomitant medications administered to the subject.

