- Highly Probable – The event follows a reasonable temporal sequence from the time of investigational device administration; and follows a known response pattern to the investigational device; and cannot be reasonably explained by other factors such as the subject's clinical state, therapeutic interventions, or concomitant medications administered to the subject; and either occurs immediately following investigational device administration, or improves on stopping the investigational device, or reappears on repeat exposure, or there is a positive reaction at the treatment site.

Each adverse event reported will be graded on a 3-point severity scale. The following definitions for rating severity will be used:

- Mild – easily tolerated, causing minimal discomfort, and not interfering with normal everyday activities.
- Moderate – sufficiently discomforting to interfere with normal everyday activities.
- Severe – incapacitating and/or preventing normal everyday activities.

**A Serious Adverse Event** is any adverse device experience that results in any of the following outcomes: death, a life-threatening adverse device experience, in-patient hospitalization or prolongation of hospitalization, a persistent or significant disability/incapacity, or a congenital anomaly/birth defect. Important medical events that may or may not result in death, be life-threatening, or require hospitalization may be considered a serious adverse device experience when, based upon appropriate medical judgment, they may jeopardize the subject or subject may require medical or surgical intervention to prevent one of the outcomes listed in this definition

If any of the above adverse events are serious as defined by the FDA Code of Federal Regulations (CFR), Title 21, special procedures will be followed. All serious adverse events will be reported within 24 hours of acknowledgment to the Medical Monitor whether or not the serious events are deemed treatment-related. All serious event reporting will adhere to 21 CFR part 812 and the IRB will be notified accordingly.

Adverse events, whether serious or non-serious, will be followed until the condition is resolved, stabilized, or otherwise explained, or the subject is lost to follow-up. Adverse events will be captured up to one week after a subject completes the study and where appropriate, medical tests and examinations will be performed to document the resolution of event(s).

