Outcomes may be classified as resolved, improved, unchanged, worse, fatal, or unknown (lost to follow-up). Following the resolution of any study-associated adverse events there will be no further adverse event reports for that subject.

**PROTOCOL DEVIATIONS:** No deviations from this protocol will be permitted, except in a medical emergency, without the approval of the Coordinating Center/Sponsor. Any amendment to this study will be discussed by the Investigators and the Coordinating Center. If agreement is reached concerning the need for modification, this will be made in a formal amendment to the protocol. All requests for protocol deviations must be approved by the IRB. If a deviation occurs, the Investigator must inform the Sponsor and IRB in writing within 10 days.

**DATA COLLECTION AND MONITORING:** The coordinating center (WashU/sponsor) will train all investigative sites. The sponsor will also monitor the site at various intervals and upon request expects to receive intermediate results by fax following each visit to evaluate treatment progress in accordance with the sponsor's monitoring procedures and guidelines. Case Report Forms and Investigator Binders will be reviewed for current data. The sponsor will collect data at the end of the follow-up period. The sponsor will list the study on clinicaltrials.gov as required by FDA regulations.

**CONFIDENTIALITY AND DISCLOSURE OF MEDICAL INFORMATION:** As part of this study the Investigator and the team at each research facility will keep records of subject participation in the study. These study records will include personal information that the subjects provide including age, sex, etc., the results of the study, information about response to treatments, and other medical information relating to participation in the study. Under federal law the study records cannot be used or disclosed by the research Investigator for research purposes unless subjects sign the informed consent authorization.

The sponsor and its consultants will analyze and evaluate study results and information and may report them to the U.S. Food and Drug Administration (the FDA) or other regulatory agencies in the United States. Study records will be assigned a code number by the study team and the subject will ordinarily not be identified by name in the study records that are sent to the Sponsor and its consultants. However, The Sponsor and its consultants will have the right to see the complete study records.

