## **Study Communications Plan**

1. Washington University School of Medicine LIFE study staff will have regularly scheduled weekly meetings.
  - a. Monthly calls will be scheduled with off-site locations
  - b. Create agenda
    - i. PI needs to approve agenda
    - ii. Email agenda to all members of the LIFE research team the day before the call
  - c. Take minutes during call
    - i. PI needs to approve the minutes
    - ii. Email minutes to all members of the LIFE research team
2. There will be regularly scheduled calls with all study sites. In the early stages of the study the calls and communications may be more frequent.
3. Any adverse events should be reported to the PI immediately.

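### One sentence in the adverse event rules ends reporting for the woman rather than for the resolved event, and contradicts the protocol's other safety reporting rules

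*Combined protocol and SAP*

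**What the plan says.** The adverse event rules stand under ADVERSE REACTIONS in the combined protocol and SAP, with one further line in the Study Communications Plan.

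- Recording: "All adverse events that occur will be recorded in the Source Documents".
- Serious events: "All serious adverse events will be reported within 24 hours of acknowledgment to the Medical Monitor", whether or not they are thought to be related to treatment.
- Follow-up of a single event: "Adverse events, whether serious or non-serious, will be followed until the condition is resolved, stabilized, or otherwise explained, or the subject is lost to follow-up".
- Capture window: "Adverse events will be captured up to one week after a subject completes the study".
- Communication: "Any adverse events should be reported to the PI immediately".
- Closure, directly after the list of outcome categories: "Following the resolution of any study-associated adverse events there will be no further adverse event reports for that subject".

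Follow-up lasts 12 months in both arms: "Participants will be contacted via telephone at 6 and 12months post enrollment to complete a follow-up survey".

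**The concern.** The closing sentence names the subject as the unit that is closed. Its trigger is resolution of a study-associated event, but what it stops is all adverse event reports for her. A woman whose mild early reaction clears would then have no later event reported, related or not, serious or not.

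The trigger would not be rare. The protocol itself expects most side effects to resolve on their own, and Risks and Benefits lists common reactions for both products.

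The LNG-IUS is being studied under an IND for a use in which the protocol says it has not been evaluated, and the device-related risks it lists are uncommon. One unreported event could therefore matter to the safety record. The protocol also forbids unapproved deviations and uses off-site enrolment staff. Two sites could follow two different sentences and each believe it was compliant.

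**Working it through.** The plan states no figure on this point, so the main check compares the text.

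**Step 1. Compare each rule with the closing sentence, read literally.**

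| Rule | Unit | When it ends | Compatible with the closing sentence? |
|---|---|---|---|
| All events recorded in source | every event | no end stated | Only if an event may be recorded and never reported, which defeats the purpose |
| Serious events within 24 hours | every serious event | no end stated | No |
| Capture window | every subject | one week after completion | No |
| Any event to the PI at once | every event | no end stated | No |
| Follow-up of an event | that event | resolved, stable, explained or lost to follow-up | Yes, but it already does what an event-level closure would do |

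No rule exempts a woman with an earlier resolved event.

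**Step 2. Test the two milder readings.**

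- *Only the resolved event is closed.* The sentence would then be redundant, because the follow-up rule already ends at resolution. It also says subject, not event.
- *Nothing more is reported once she has left the study and her open events have resolved.* This fits the position of the sentence, which comes shortly after the capture window. It would remove the conflict, but the sentence contains no reference to study exit.

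**Step 3. How much follow-up is exposed for one woman.** Take 12 months as 52 weeks. The capture window is 52 + 1 = 53 weeks. If her event resolves at week *t*, the literal rule closes 53 − *t* weeks. The documents give no *t*, so these values are assumptions:

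- *t* = 2: 51 weeks closed
- *t* = 26: 27 weeks closed
- *t* = 52: 1 week closed

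**Step 4. Can a difference between arms be derived?** Risks and Benefits lists reaction rates of 18, 12, 12, 9, 6 and 5% for UPA, and 51.9, 23.9, 23.4, 12.8 and 12% for the LNG-IUS. Assuming the reactions are independent, the chance of at least one listed reaction is:

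- UPA: 1 − (0.82 × 0.88 × 0.88 × 0.91 × 0.94 × 0.95) = 48.4%
- LNG-IUS: 1 − (0.481 × 0.761 × 0.766 × 0.872 × 0.88) = 78.5%

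Without independence, the ranges are 18% to 62% for UPA and 51.9% to 100% for the LNG-IUS. The lower end is the largest single rate. The upper end is the sum of the rates, capped at 100%.

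Closure also needs resolution. Let *r* be the share of these women whose event resolves before a later event occurs. The share closed is the probability above times *r*. The documents give no *r*:

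- *r* = 0.5 in both arms: 24.2% UPA, 39.2% LNG-IUS
- *r* = 0.9 for UPA and 0.4 for LNG-IUS: 43.6% UPA, 31.4% LNG-IUS

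The order reverses within plausible assumptions, so neither size nor direction can be fixed.

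**Step 5. What other data collection would recover.** Under Evaluation/Follow-Up, the telephone surveys ask about new diagnoses, interval pregnancies and interval STIs in both arms. Risks and Benefits sets a DSMB trigger for pregnancies in the LNG-IUS arm, and the Pregnancy section sets a work-up for a positive test. These would bring some later events to light. The surveys do not in themselves provide the relatedness assessment, severity grade or 24-hour notice that the adverse event rules require.

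**The case against.** The strongest reply is that the sentence has been lifted out of its sequence. The text moves from the capture window, to tests that document resolution, to outcome categories, and then to closure. Read in that order, and noting the plural in the sentence, it can mean that a woman's file closes once she has completed the study and nothing remains open. A site would also have to put this one sentence above four clear rules before it dropped a late infection, perforation or pregnancy complication.

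Part of this stands. The post-exit meaning is possible and may well be what was intended, and the other rules make heavy under-reporting less likely. But it has to be supplied by the reader, and the sentence would need rewording even if that meaning is correct.

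A reader might go further and infer that later events would be lost unequally, in favour of the LNG-IUS, because its listed reactions are more frequent and only that arm has an extra visit ("Women randomly assigned to the LNG-IUS group will be asked to return at 5-6 weeks for a string check"). The documents do not support this. The rates carry no timing, no resolution times are given for either arm, and a reaction that persists while the device is in place would not trigger closure at all. The statistical sections also plan no comparison of adverse events between arms.

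**Conclusion.** The contradiction is real. Taken literally, the closing sentence ends reporting for the woman, while the capture window, the serious event rule and the instruction to inform the PI all require new events to be reported regardless of her history. A site that followed it could miss new events during the 12-month follow-up and the week after.

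This depends on a site applying the sentence as written. For one woman, the exposure could be most of the window. For the trial as a whole, the number of lost reports cannot be estimated, because the documents give neither event times nor resolution times. For the same reason no claim of bias between arms is made, and the reaction rates in step 4 must not be read as counts of women closed to reporting. The surveys and pregnancy procedures limit the loss. The primary pregnancy outcome is collected separately and is not affected.

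This is an inconsistency in a safety rule that should be corrected. It is not a flaw in the trial's main comparison.

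**What to change.** Delete the closing sentence, or limit it to the event, for example: once an adverse event has resolved, no further reports are required on that event. Then state in the same place that all new adverse events, in both arms and whatever a woman's earlier events, are captured and reported up to one week after she completes the study, as the capture window already requires. If closure of the file after study exit was the intent, say so and give the time from which it applies.

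The cost is one sentence, and a note to the sites if they have been trained on the current text. Sample size, visits and analyses do not change.

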## Study Devices and Medications

### Package Inserts:

#### LNG-IUS

<http://www.fda.gov/downloads/Drugs/DevelopmentApprovalProcess/DevelopmentResources/UCM245685.pdf>

#### Ulipristal Acetate

[http://www.accessdata.fda.gov/drugsatfda\\_docs/label/2010/022474s000lbl.pdf](http://www.accessdata.fda.gov/drugsatfda_docs/label/2010/022474s000lbl.pdf)

## Risks and Benefits

The interventions compared in this trial are oral UPA versus LNG-IUS. No serious or life-threatening adverse events are expected. Nonetheless, the following measures will be taken to monitor and investigate adverse events. Immediate EC failures should be uncommon. If more than one pregnancy occurs in the LNG-IUS arm, an urgent DSMB meeting will be convened to discuss the preliminary outcomes. These immediate failures must be put into context of the number of long-term (6 and 12-month) failures to determine if the trial will continue.

According to the Prescribing Information, the most common adverse reactions ( $\geq 5\%$ ) to UPA are headache (18%), abdominal pain (12%), nausea (12%), dysmenorrhea (9%), fatigue (6%), and dizziness (5%). The most common adverse reactions to the LNG-IUS reported in clinical trials ( $> 10\%$  users) are uterine/vaginal bleeding alterations (51.9%), amenorrhea (23.9%), intermenstrual bleeding and spotting (23.4%), abdominal /pelvic pain (12.8%) and ovarian cysts (12%). With any IUD insertion, there are risks of infection (<1%) and uterine perforation (approximately 0.1%).

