### **Power Analysis and Sample Size**

Power analysis and Sample size calculation was performed with Epi-Info v 6.0.

**Sample Size:** With an alpha ( $\alpha$ ) = 0.05, power of 90%, and assuming unintended pregnancy rates (total 5 weeks through 6 months) of 11% for the oral UPA regimen and 2% for the LNG-IUS, and a 3:1 ratio of LNG-IUS allocation to UPA, we calculate our sample size to be 532 participants (399 LNG-IUS and 133 UPA). This accounts for approximately 20% loss to follow-up rate by 6 months. We chose a 3:1 ratio of LNG-IUS to UPA to allow for a more precise estimate of immediate failure rates of the LNG-IUS group.

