### **Enrollment**

## Clinic visit (30-45 minutes approximately)

- Participant is directed to an enrollment room and given a copy of the *Informed Consent* to read
- Research assistant logs into RedCap, allowing the participant to read the consent paperwork
- Research assistant goes over the consent document allowing the participant to ask questions
- Consents are signed and dated
- Participant is directed to the clinic restroom with instructions given to provide a urine sample for the *Urine Pregnancy Test (UPT)*; and the *self-administered swabs* for chlamydia and gonorrhea testing
- Return to enrollment room and wait for UPT test results to determine eligibility for enrollment
- If participant is not currently pregnant the contact information form, baseline enrollment questionnaire, and clinical enrollment forms are completed
- Randomization to method of Emergency Contraception (EC) is determined
- Participant is directed to clinic waiting room
- Research assistant confers with clinician
- If randomized to oral EC,
  - Participant is given the pills and a cup of water and research assistant observes the participant taking the pill
  - A prescription for refillable oral contraceptive pills is offered
  - Tax forms are filled out and gift card is offered
  - Participant is given UPT to take home
  - Participant is reminded that she will be called for first follow-up in 4-5 weeks
- If randomized to LNG-IUS,
  - Participant is directed to a clinic exam room
  - Clinician performs pelvic exam to determine if there is evidence of cervicitis
  - If no cervicitis is present the LNG-IUS will be inserted by a properly-trained clinicians
  - Tax forms are filled out and a gift card is offered
  - Participant is given UPT to take home
  - Participant is reminded that she will be called for first follow-up in 4-5 weeks

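### Is the DSMB trigger of more than one LNG-IUS pregnancy unusable because it names no time window and no denominator?

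*Combined protocol and SAP*

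**What the plan says.** The trigger is in the Risks and Benefits section of the combined protocol and SAP: "If more than one pregnancy occurs in the LNG-IUS arm, an urgent DSMB meeting will be convened to discuss the preliminary outcomes". The sentence before it reads "Immediate EC failures should be uncommon". The sentence after it reads "These immediate failures must be put into context of the number of long-term (6 and 12-month) failures to determine if the trial will continue".

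The notion of an immediate failure appears once more, under Power Analysis and Sample Size, where the 3:1 allocation is chosen "to allow for a more precise estimate of immediate failure rates of the LNG-IUS group". It is not defined there either. The same section plans the trial "assuming unintended pregnancy rates (total 5 weeks through 6 months) of 11% for the oral UPA regimen and 2% for the LNG-IUS", with 399 women allocated to the LNG-IUS and about 20% lost by 6 months.

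The first follow-up is worded in three ways:

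- Research Design and Methodology: participants "will be called to report the results of the urine pregnancy test 5-6 weeks after insertion".
- Evaluation/Follow-Up: participants "will be called at 5 weeks post enrollment to obtain results".
- The enrolment clinic visit in the study flow: "Participant is reminded that she will be called for first follow-up in 4-5 weeks".

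**The concern.** Taken alone, the trigger is a bare count with no time limit. If it covered every pregnancy reported through 6 months, the plan's own 2% rate would make an urgent meeting almost inevitable, and the alarm would carry no information. If it covers only immediate failures, the reader has to work out what immediate means, and the natural anchor, the first follow-up, has three timings.

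Three smaller questions follow:

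- Two failures mean something different among 100 women than among 399, and the text does not say that the numbers assessed go to the DSMB.
- The arm could mean all women randomised to the LNG-IUS or only those who received it. The check for cervicitis comes after randomisation, so the two groups can differ.
- A pregnancy found between contacts needs a basis for deciding which period it belongs to.

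What is at stake is whether the DSMB is called for the right reason and can interpret what it sees, since the meeting bears on whether the trial continues.

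**Working it through.** **Which pregnancies are counted.** The sentences on both sides of the trigger concern immediate failures, and the second contrasts them with 6- and 12-month failures. The Retention Plan and the study flow list three outcome contacts: 5 weeks, 6 months and 12 months. The Primary Outcome paragraph uses 5 weeks and 6 months. With 6 and 12 months set aside as long-term, only the 5-week contact remains.

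**How far apart the timings are.** The windows 4-5, 5 and 5-6 weeks all contain week 5 and together span two weeks. The 4-5-week version is only what the participant is told at enrolment. The study flow heads the contact itself as the 5-week follow-up.

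**How the trigger behaves.** The plan gives no operating figure for the trigger, so there is none to reproduce. Inputs:

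- Women in the LNG-IUS arm: n = 399 (Power Analysis and Sample Size), or 0.8 × 399 = 319 after 20% loss. The number assessed at 5-6 weeks should lie between these.
- Copper IUD: 99% reduction in pregnancy risk (Background & Significance). The Pregnancy section hypothesises that the LNG-IUS will match it.
- UPA: 93-94% effective (Pregnancy section).
- Untreated pregnancy risk: not in the documents. Assumed 5%, 10% or 20%.

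Immediate failure rate: p = untreated risk × (1 − effectiveness). Probability that the trigger fires:

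P(X ≥ 2) = 1 − (1 − p)^n − n·p·(1 − p)^(n−1)

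Example with 10% untreated risk and a copper-like device: p = 0.10 × 0.01 = 0.001. For n = 399, P = 1 − 0.6709 − 0.2679 = 0.061. For n = 319, P = 1 − 0.7268 − 0.2321 = 0.041.

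| Assumed untreated risk | Effectiveness | p | P(fires), n = 319 | P(fires), n = 399 |
|---|---|---|---|---|
| 5% | 99% | 0.05% | 1.1% | 1.7% |
| 5% | 94% | 0.30% | 24.8% | 33.6% |
| 5% | 93% | 0.35% | 30.7% | 40.7% |
| 10% | 99% | 0.10% | 4.1% | 6.1% |
| 10% | 94% | 0.60% | 57.1% | 69.1% |
| 10% | 93% | 0.70% | 65.4% | 76.9% |
| 20% | 99% | 0.20% | 13.4% | 19.0% |
| 20% | 94% | 1.20% | 89.6% | 95.3% |
| 20% | 93% | 1.40% | 93.8% | 97.6% |

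At each assumed risk, the trigger separates a device that works as hypothesised from one no better than the oral comparator.

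**The literal reading, for contrast.** With all pregnancies through 6 months at p = 2%, the expected counts are 319 × 0.02 = 6.4 and 399 × 0.02 = 8.0. The trigger fires with probability 98.8% and 99.7%. The 2% is cumulative to 6 months, so it does not conflict with a trigger on immediate failures.

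**What the denominator adds.** Two failures with exact (Clopper-Pearson) 95% intervals:

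- 2/100 = 2.0% (0.2-7.0%)
- 2/319 = 0.6% (0.08-2.3%)
- 2/399 = 0.5% (0.06-1.8%)

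The denominator matters for interpreting the count at the meeting, not for deciding whether to call it.

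**Timing.** Taking 6 months as 26 weeks and 12 months as 52, a failure found at 5-6 weeks is detected 20-21 weeks before that woman's 6-month contact (26 − 6, 26 − 5) and 46-47 weeks before her 12-month contact (52 − 6, 52 − 5). How much long-term information a meeting would have depends on accrual, which the documents do not give.

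**The case for a change.** The best case for a change is that this is the only numerical DSMB trigger in the documents, that it bears on continuation, and that one clause would rule out the uninformative reading. It is true that no sentence defines an immediate failure, that the first follow-up is worded inconsistently, that randomised versus inserted is not spelled out, and that the numbers to be shown to the DSMB are not listed. A tidy-minded author would settle these in a few lines.

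None of it shows that the trigger would be misapplied:

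- **Uneven reporting by site.** The Data Management paragraph has all telephone follow-up surveys done by the coordinating university's staff, and the first pregnancy result is obtained by such a call. Routine ascertainment is therefore central. Sites may confirm positive tests, but nothing suggests they would apply windows of their own.
- **Pregnancies between contacts.** Data Analysis/Statistical Methods dates pregnancies from the last menstrual period for the Kaplan-Meier comparison, and the Pregnancy section provides ultrasound dating. Neither is tied to the trigger in words, but both give a basis for placing a pregnancy.
- **Randomised or inserted.** A trial arm ordinarily means the women randomised to it. The distinction matters only if a woman assigned to the LNG-IUS but not given it becomes pregnant, and the documents give no frequency for that.
- **Denominators.** The DSMB meets to discuss preliminary outcomes. Nothing implies that counts would come without numbers assessed, and such detail normally sits in a charter, which is not among these documents.

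**Conclusion.** The concern does not call for a change. The wording is loose, but the text around the trigger and the contact schedule fix its meaning as failures found at the roughly 5-week assessment. On that reading the rule does its job: a copper-like device fires it with probability 1-19% and a UPA-like device with 25-98%, across assumed untreated risks of 5-20% and 319-399 women assessed. Those ranges rest on the assumed untreated risk. At any single assumed value the two devices are clearly apart, for example 4-6% against 57-77% at 10%. The 98.8-99.7% figure belongs only to a literal reading that the context does not support.

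The rule convenes a meeting and is not a stopping boundary, so a bare count is enough to raise the alarm. The sample size, alpha, power and effect estimate are unaffected. What remains is a missing label and routine reporting detail, which analysts or a DSMB charter would supply in the ordinary course.
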